## **3.10. Other Analyses**

### **3.10.1. Participant Disposition**

The number of patients who were screened, randomized, completed scheduled follow up, and prematurely withdrew study participation will be summarized overall and by treatment group. Reasons for screen failure and for withdrawal from study will be presented.

### **3.10.2. Study Drug Compliance and Tolerance**

The number of days of exposure to study drug will be summarized by treatment group. Compliance with study drug will be calculated as the number of doses taken divided by the scheduled number of doses taken prior to permanent discontinuation, expressed as a percentage. Compliance will be summarized overall and by 4-week interval for each treatment group. Time to discontinuation of study drug will be estimated using Kaplan-Meier product-limit estimates. Treatment-dependent differences will be tested by log-rank test.

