	
randomized to SYN120 100 mg QD will receive two 10 mg tablets for the first 7 days, one placebo tablet and one 50 mg tablet for the next 7 days, and two 50 mg tablets every day for the remaining 14 weeks. Participants randomized to placebo will receive the same number of placebo tablets on the same titration schedule.
 
After randomization, patients will be evaluated at clinic visits at Week 4 (28 ± 3 days), Week 8 (56 ± 3 days), and Week 16 (112 ± 3 days), and again 2 weeks (14 ± 3 days) following the Week 16 Visit (or at Early Termination, if applicable). Patients will also be contacted by the study site by telephone at Week 2 (14 ± 3 days) and Week 12 (84 ± 3 days) for assessment of AEs.
 
At the clinic visits, patients will be asked to bring their study drug to the study site. Blood pressure and pulse (supine and standing) will be measured at each outpatient visit. Patients will be assessed for safety and tolerability in a blinded fashion regularly throughout the study and 2 weeks after their last dose of study drug.
 
Please refer to the Schedule of Events/Evaluations in Table 1 for specific timing of assessments.

Criteria for Withdrawal from Study	
Investigational medicinal product may be discontinued for a given participant at any time if clinically significant out-of-range laboratory values or clinically significant abnormal findings on physical examination or intolerable AEs put the patient at additional risk, as judged by the Investigator.
 
Patients will also discontinue IMP if their cognitive dysfunction or motor function worsens to the extent that in the judgment of the Investigator they require the addition of new medication to control their symptoms.
 
Patients may withdraw consent and discontinue from the study for any reason.
 
The Study Sponsor (Biotie Therapies) has the right to terminate the study at any time.
 
All patients who withdraw consent prematurely will be requested to return for an onsite visit that includes all safety procedures as outlined for early termination in Table 1. For any early discontinuation, the patient should be requested to return for a Safety Follow Up Visit 2 weeks after the last dose of study drug, unless the Early Termination Visit itself occurs 2 or more weeks after the last dose of study drug.

PROTOCOL SYNOPSIS	

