Statistical Analysis	
Primary Outcome Variable
 
The primary analysis will be performed on the mITT analysis set and will use a shared-baseline repeated measures ANOVA that includes fixed effects for visit and the interaction between treatment group and post-baseline visit, random center-specific intercepts, and unstructured within-person covariance.
 
Secondary and Exploratory Outcome Variables
 
Outcomes that are approximately normally distributed will be analyzed as described above for the primary outcome variable. Outcomes that are not normally distributed will be transformed or compared between the treatment groups using a van Elteren test that incorporates stratification by center. The key secondary outcome of CDR Quality of Episodic Memory will be tested for significance using the mITT analysis set at two-tailed alpha = 0.05. Other secondary outcomes will also be tested at two-tailed alpha = 0.05 using the mITT analysis set, recognizing that the totality of results will be evaluated in judging the potential of SYN120 as a therapeutic agent for PDD.
 
Safety Analysis
 
The assessment of safety will focus on the frequencies of individual AEs, vital signs (particularly orthostatic hypotension), UPDRS, abnormal laboratory test results, and ECG abnormalities, particularly treatment-emergent events. The frequency and type of any observed suicidal ideation will be described. The analyses will use the SS, Fisher's exact test for comparison of the proportion of participants in each treatment group experiencing a given AE or abnormal finding, and negative binomial regression for total counts of AEs.
 
Tolerability
 
Tolerance to SYN120 will be evaluated by recording the proportion of participants who discontinue IMP and by testing for a treatment-dependent difference in the time to discontinuation.

Table 1: Schedule of Events/Evaluations

Assessments	Study Visit	Study Period	Screening ^a	Baseline Predose	16-Week Treatment Period (Double-blinded Dosing) (Days 1-112)						Safety Follow Up (Post Dose Follow Up)	Early Term.	Unscheduled	
					0	2 (±3 days)	4 (±3 days)	8 (±3 days)	12 (±3 days)	16 (±3 days)	18 (± 3 days)			
					−6 to −1	V3 (phone call)	V4	V5	V6 (phone call)	V7	V8	V99	V98	
Onsite clinic visit			X	X		X	X			X	X	X		X
Obtain patient and caregiver informed consent			X											
Demographics; medical history including neurological and PD/PDD history			X											

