2.2.6 Tolerability

Tolerability of SYN120 will be evaluated using the following measures:

1. Proportion of participants discontinuing IMP.
2. Proportion of participants discontinuing IMP due to an AE.
3. Time to discontinuation of IMP.

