### 3.2.3. Tolerability Endpoint

Participants will be judged tolerant of study drug if they complete their week 16 visit without prior permanent discontinuation of study drug and without prior study drug suspension lasting longer than 14 days. Tolerability will be summarized as the proportion of participants in a treatment group who are tolerant of study drug.

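### The SAP's tolerability endpoint and its only tolerance test count stops for any cause, and the protocol's AE-specific discontinuation measure is left out of both

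*SAP*

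**What the plan says.** SAP 3.2.3 defines the endpoint: "Participants will be judged tolerant of study drug if they complete their week 16 visit without prior permanent discontinuation of study drug". A drug interruption of more than 14 days also makes a participant intolerant. Reason plays no part. The endpoint is descriptive: "Tolerability will be summarized as the proportion of participants in a treatment group who are tolerant of study drug". No test is named for it.

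SAP 3.10.2 plans: "Time to discontinuation of study drug will be estimated using Kaplan-Meier product-limit estimates". The arms are then compared with a log-rank test. The section sets no cause restriction and no rule for stops due to worsening. The protocol synopsis presents the same comparison as the tolerability test ("by testing for a treatment-dependent difference in the time to discontinuation").

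The synopsis, under criteria for withdrawal, says: "Patients will also discontinue IMP if their cognitive dysfunction or motor function worsens". The threshold there is a need for new medication. Protocol 4.3.1 is softer and narrower. It lists worsening of PDD symptoms among events that may lead to a stop after discussion with the Medical Monitor, and does not list motor worsening.

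Protocol 2.2.6 names three tolerability measures: all discontinuation, "Proportion of participants discontinuing IMP due to an AE", and time to discontinuation. The second appears in neither SAP 3.2.3 nor SAP 3.10.2. SAP section 1 makes the SAP authoritative where the two documents conflict on analysis.

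SAP 3.2.2(e) and 3.9.1 report, by arm and without a test, TEAEs leading either to permanent drug discontinuation or to early termination. They also classify TEAEs by action taken with study drug.

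**The concern.** Tolerability is a stated objective, and the log-rank test is the only between-arm test that the SAP sets for it. Its null hypothesis is equal hazard of stopping for any reason. That differs from equal intolerance when lack of efficacy is itself a route to stopping.

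If SYN120 helps cognition, worsening stops should be fewer on SYN120 than on placebo, and they pull the all-cause comparison against any excess of AE stops on SYN120. The distortion grows with the benefit, which is the case in which the sponsor would want a clear tolerability result. The reverse error is also possible: equal AE stopping with fewer worsening stops on SYN120 would read as better tolerability.

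**Working it through.** **The plan's own figure.** The only sizing is for the primary endpoint: effect size 0.69, two-sided 0.05, 80% power, 15% loss. The normal approximation gives 33 per arm; 33 / 0.85 = 38.8, so 39 per arm or 78 in total, against the stated 80. At 40 × 0.85 = 34 evaluable per arm, t-test power is 80.05%. It reproduces and is not in dispute. The documents give no power figure and no stop rates by reason for tolerability, so **every rate below is an assumption**.

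**Model.** 40 per arm, 16 weeks, independent exponential times to AE, worsening and other stops, with other stops at 5% per arm. Weekly hazard h = −ln(1 − p)/16 for a 16-week net risk p. The all-cause hazard ratio (HR) is the sum of the three hazards on SYN120 over the sum on placebo; the factor 1/16 cancels. Example: AE 20% v 5%, worsening 2% v 17% (SYN120 v placebo throughout).

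- SYN120: 0.2231 + 0.0202 + 0.0513 = 0.2946
- Placebo: 0.0513 + 0.1863 + 0.0513 = 0.2889
- All-cause HR 0.2946 / 0.2889 = 1.02; AE-specific HR 0.2231 / 0.0513 = 4.35

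**Dilution and offset.** Simulated chance of a significant log-rank result showing more stops on SYN120. The AE-specific test censors stops for other reasons.

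| AE stops | Worsening stops | All-cause HR | Planned test | AE-specific test |
|---|---|---|---|---|
| 15% v 5% | 2% v 5% | 1.52 | 11% | 30% |
| 15% v 5% | 2% v 12% | 1.02 | 3% | 30% |
| 20% v 5% | 10% v 10% | 1.83 | 26% | 51% |
| 20% v 5% | 5% v 15% | 1.23 | 6% | 50% |
| 20% v 5% | 2% v 17% | 1.02 | 3% | 50% |
| 30% v 5% | 2% v 20% | 1.31 | 10% | 85% |

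Equal worsening rates dilute the comparison without reversing it. Full cancellation needs worsening stops to differ by about as much as AE stops, in the opposite direction.

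**False tolerability signal.** AE stops equal in the two arms (5% each; 8% each in the 5% v 25% row).

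| Worsening stops | Planned test rejects |
|---|---|
| 1% v 3% | about 6% |
| 2% v 5% | about 6% |
| 5% v 10% | about 8% |
| 5% v 15% | 18% |
| 5% v 20% | 31% |
| 5% v 25% | 43% |
| 10% v 30% | 44% |

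In the last four rows nearly all rejections favour SYN120, and the AE-specific test rejects between 2.5% and 4.5% of the time.

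**Overlap of worsening and AE.** Protocol 8.1 allows clinically significant worsening of the disease to be recorded as an AE. If every worsening stop is also an AE stop, the AE-specific test loses its advantage. With AE stops 25% v 5% and worsening 5% v 15%, it has 16% power against 14% for the planned test, where clean separation gives about 71%. With equal AE stops of 5% and worsening 5% v 15%, it gives a false signal 23% of the time against 18%.

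**Limits of an AE-specific test.** For HR 3 and 80% power it needs 27 events (Schoenfeld) to 32 (Freedman). Ignoring competing stops, AE risks of 15% v 5% yield 40 × 0.15 + 40 × 0.05 = 8 events, and 30% v 5% yield 14. As an estimate, 15% v 5% is a difference of 10 points with standard error √(0.15 × 0.85/40 + 0.05 × 0.95/40) = 0.066, so a 95% interval of roughly −3 to 23 points.

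**The case against.** The strongest reply has four parts.

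- **AE-led stops are already visible by arm.** This stands. With 5% v 25%, about 2 and 10 patients would appear in the SAP 3.2.2(e) and action-taken tables. A reader might infer that an AE excess would be concealed; the documents do not support that. What can mislead is the result labelled tolerability and its p-value.
- **All-cause discontinuation and time to discontinuation are the protocol's own tolerability measures.** This also stands, so the log-rank test is not an error to be removed. The protocol lists the AE-specific measure beside them, however, and the SAP tolerability sections do not.
- **Worsening and AE stops are not cleanly separable, and motor worsening is not simply lack of efficacy.** This stands. UPDRS is a safety measure and no efficacy endpoint is motor, so censoring motor stops could hide harm. It rules out replacing the all-cause result with a purely AE-specific one, and calls for a stated overlap rule.
- **The large effects need large worsening differences within 16 weeks, and the AE-specific test is weak at this size.** Both are true. Dilution, however, already appears at 2% v 5% worsening (11% v 30% power).

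Two further inferences go too far. The log-rank test is not a test of the SAP 3.2.3 proportion, which has none and also counts suspensions over 14 days. And stops for worsening are stated as mandatory only in the synopsis, not in Protocol 4.3.1.

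**Conclusion.** The point holds in limited form. SAP 3.2.3 and 3.10.2 measure all-cause persistence on study drug, and the protocol's AE-discontinuation measure has no place in the SAP tolerability endpoint and no planned between-arm comparison. The planned test can therefore understate an AE-driven difference, or credit efficacy as tolerability.

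The size is conditional on assumed rates: from modest dilution when worsening stops are few or balanced, to near-complete cancellation (about 3% power) when worsening and AE differences are equal and opposite. False signals stay at about 6% to 8% for worsening differences up to 5% v 10%. The advantage of an AE-specific analysis also depends on worsening stops not being classed as AE stops. It should be added for estimation and interpretation; it will not be a well-powered test at 40 per arm.

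**What to change.** Before unblinding, amend the SAP as follows.

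1. Keep the tolerant proportion, Kaplan-Meier curve and log-rank test, labelled *all-cause persistence on study drug*.
2. Add discontinuation of IMP due to an AE as a named tolerability endpoint in 3.2.3 and 3.10.2, with the SYN120-minus-placebo difference in the 16-week proportion and its 95% confidence interval.
3. Show cumulative incidence by arm and reason (AE, cognitive worsening, motor worsening, other), treating the other reasons as competing events.
4. Classify by the primary reason that Protocol 4.3.2 requires in the eCRF. State a rule for worsening stops also recorded as AEs, and add a sensitivity analysis that counts these, and motor-worsening stops, as AE stops.
5. In 3.2.2(e), report AE-related drug discontinuation separately from AE-related early termination.

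The synopsis and Protocol 4.3.1 differ on both the force and the scope of stopping for worsening and must be reconciled, since this determines which stops enter the analysis.

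The cost is SAP wording, one table and one figure, from data already collected. The drawbacks are few events and reliance on the investigator's blinded attribution of the reason, which is why the all-cause result stays alongside.

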### **3.10.3. Prior and Concomitant Medication Use**

All prior and concomitant medications taken during the study period will be listed for each patient, including dosage and indication. Each medication will be coded using the World Health Organization Drug Dictionary Enhanced and classified as a past medication (last dose taken prior to the first dose of study drug), a concomitant medication ongoing at baseline, or a concomitant medication initiated after baseline. The percentage of patients taking each medication (or class of medications) will be summarized overall and by treatment group.

### **3.10.4. Pharmacokinetic Samples**

Results of the plasma assays of SYN120 will be descriptively analyzed by treatment group and visit. Population estimates of  $C_{\max}$ ,  $t_{\max}$ , and half-life will be estimated based on self-reported time since last dose of study drug. Separate population analysis on the data from this study alone or combined with data from other studies as deemed appropriate will be performed and reported separately.

## **3.11. Handling of Protocol Deviations**

Important protocol deviations are deviations from the protocol which could have a meaningful impact on either the primary efficacy or safety endpoints. The criteria for identifying important protocol deviations and the classification of important protocol deviations will be defined prior to unblinding. To the extent feasible, rules for identifying protocol deviations will be defined without review of the data and without consideration of the frequency of occurrence of such deviations. Whenever possible, criteria for identifying important protocol deviations will be implemented algorithmically to ensure consistency in the classification of important protocol deviations across all patients.

